2) Physician's Global Assessment (PGA)

Record the presence or absence of assessment, assessment date, results of assessment at the start date of administration, Week 24 and 52 after the start of administration, or withdrawal/termination.

The PGA is a 0-10 cm visual analogue scale (VAS). The investigator will assess the patient's global disease activity, and draw a vertical line between 0 CCI and 3 CCI (See Appendix 2).

0 : CCI

1 : CCI

2 : CCI

3 : CCI

3) Assessment of Daily Living by Lupus Impact Tracker

Record the presence or absence of assessment, assessment date, results of assessment at the start date of administration, Week 24 and 52 after the start of administration, or withdrawal/termination.

The investigator will interview patients about their conditions in the previous one month using Lupus Impact Tracker, the impact on daily living will be assessed using a 5-point scale of 0 CCI to 4 CCI

CCI - This section contained Clinical Outcome Assessment data collection questionnaires or indices, which are protected by third party copyright laws and therefore have been excluded.

* 0 : CCI 1 : CCI 2 : CCI
3 : CCI 4 : CCI

12. Laboratory tests

1) Monitoring for TB (if a patient has TB as a past history)

Presence or absence, test date, results of chest image test and interferon-gamma release assay (The chest image test includes the presence or absence of findings of activity.)

2) Monitoring for HB (if a patient is a HB virus carrier or has a past HB infection)

- Presence or absence, test date, results of HBV-DNA quantification test and hepatic function test (aspartate aminotransferase (AST), alanine aminotransferase (ALT))
- 3) The information about the following items will be collected.
- Presence or absence of assessment, assessment date, results of assessment at the start date of administration*, Week 24 and 52 after the start of administration, or withdrawal/termination
- * : If no information is available about the results of assessment at the start date of administration, record the information closest to the start date in the results of SLE diagnosis to the start date.
- i) Immunological test
Anti-double-stranded DNA (anti-dsDNA) antibody, C3, C4, CH50
 - ii) Renal function test
Protein/creatinine ratio
13. Continuation status of Benlysta administration at the end of the observation period

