- The necessity for creation of the Risk Minimization Plan for a new concern in the safety specification will be considered.

14. Publication of the Study Results

The information regarding the results of the study will be provided to clinical sites as an interim report and a final report as appropriate for the purpose of “proper use” and “safety assurance”, considering a proper timing and the number of patients whose CRF is collected, etc., by means of presentation at academic conferences and papers.

In addition, the summaries of the plan and results in the study will be disclosed in GSK Clinical Study Register.

15. Other Requirements

1. Protocol revision

The progress in the study, the number of patients excluded from analysis, occurrence of unexpected/serious ADRs, large increase in occurrence of specific ADRs and validity of the study items, etc. will be timely grasped during the study period, and the Protocol will be reviewed and revised if required.

If the content of the Protocol in the study has been changed, the Change Notification should be submitted to the PMDA in advance, except for minor changes.

2. Measures to be taken in detecting issues or concerns

If issues, etc. have been detected from the results of assessment/analysis during the study period or after completion of the study, consideration will be given on whether or not the SDUI or Post-marketing Clinical Study should be newly conducted, as appropriate.

16. Attachments

- | | |
|---|------|
| 1) Organizational Structure for Post-marketing Surveillances | AT 1 |
| 2) BENLYSTA for Intravenous Injection / Subcutaneous Injection SDUI
Written Contract | AT 2 |
| 3) BENLYSTA for Intravenous Injection / Subcutaneous Injection SDUI
Implementation Guidance | AT 3 |
| 4) BENLYSTA for Intravenous Injection / Subcutaneous Injection SDUI
Enrolment Form | AT 4 |
| 5) BENLYSTA for Intravenous Injection / Subcutaneous Injection SDUI
Case Report Form 1 | AT 5 |
| 6) BENLYSTA for Intravenous Injection / Subcutaneous Injection SDUI/
Case Report Form 2 | AT 6 |
| 7) BENLYSTA for Intravenous Injection / Subcutaneous Injection SDUI
Follow-up Investigation Case Report Form | AT 7 |

Appendix 1

SELENA SLEDAI INSTRUMENT SCORE (From [Petri, N Engl J Med 2005])

Wt	Descriptor	Definition
8	Seizure	Recent onset (last 10 days). Exclude metabolic, infectious or drug cause, or seizure due to past irreversible CNS damage.

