8	Psychosis	Altered ability to function in normal activity due to severe disturbance in the perception of reality. Include hallucinations; incoherence; marked loose associations; impoverished thought content; marked illogical thinking; bizarre, disorganized or catatonic behavior. Exclude uremia and drug causes.
8	Organic brain syndrome	Altered mental function with impaired orientation, memory or other intellectual function, with rapid onset and fluctuating clinical features. Include clouding of consciousness with reduced capacity to focus, and inability to sustain attention to environment, plus at least 2 of the following: perceptual disturbance, incoherent speech, insomnia or daytime drowsiness, or increased or decreased psychomotor activity. Exclude metabolic, infectious or drug causes.
8	Visual disturbance	Retinal and eye changes of SLE. Include cytoid bodies, retinal hemorrhages, serous exudate or hemorrhages in the choroid, optic neuritis, scleritis or episcleritis. Exclude hypertension, infection or drug causes.
8	Cranial nerve disorder	New onset of sensory or motor neuropathy involving cranial nerves. Include vertigo due to lupus.
8	Lupus headache	Severe persistent headache: may be migrainous, but must be nonresponsive to narcotic analgesia.
8	CVA	New onset of cerebrovascular accident(s). Exclude arteriosclerosis or hypertensive causes.
8	Vasculitis	Ulceration, gangrene, tender finger nodules, periungual infarction, splinter hemorrhages, or biopsy or angiogram proof of vasculitis.
4	Arthritis	More than 2 joints with pain and signs of inflammation (i.e., tenderness, swelling or effusion).
4	Myositis	Proximal muscle aching/weakness, associated with elevated creatine phosphokinase/aldolase or electromyogram changes or a biopsy showing myositis.
4	Urinary casts	Heme-granular or red blood cell casts.
4	Hematuria	>5 red blood cells/ high power field. Exclude stone, infection or other cause.
4	Proteinuria	New onset or recent increase of more than 0.5 gm/24 hours.
4	Pyuria	>5 white blood cells/ high power field. Exclude infection.
2	Rash	Ongoing inflammatory lupus rash.
2	Alopecia	Ongoing abnormal, patchy or diffuse loss of hair due to active lupus.
2	Mucosal ulcers	Ongoing oral or nasal ulcerations due to active lupus.
2	Pleurisy	Classic and severe pleuritic chest pain or pleural rub or effusion or new pleural thickening due to lupus.
2	Pericarditis	Classic and severe pericardial pain or rub or effusion, or electrocardiogram confirmation.

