4.10. Responders

A responder is defined as a case where this drug treatment start date and post-treatment assessments are present and the following conditions are met:

Efficacy assessments	Responder definition
SELENA SLEDAI (Used for calculation of efficacy percentage)	≥ 4 decrease in score from baseline
PGA score	≥ 0.3 (10 mm) decrease from baseline
LLDAS (Lupus Low Disease Activity State)	1. SELENA-SLEDAI ≤ 4 and no major active organ involvement (renal, central nervous system, cardiopulmonary, vasculitis, pyrexia) on SELENA-SLEDAI, without hemolytic anemia or active gastrointestinal lesions reported as adverse events.
	2. No new signs or symptoms as compared to the last SELENA-SLEDAI assessment.
	3. PGA score ≤ 1 (33 mm)

Efficacy assessments	Responder definition
	4. Corticosteroid dose ≤ 7.5 mg/day at time of assessment
	5. Use of the same immunosuppressant as compared with prior medication. No unapproved drugs of rituximab, anifrolumab, ustekinumab, or baricitinib are used as concomitant medications. The use of anifrolumab with this drug initiated on 2021/9/27 or later is allowed.
LLDAS Adverse Events	Haemolytic anaemia: 10018916 (PT code) Active gastrointestinal lesions: to be defined in a separate document
Corticosteroid Reduction at Week 40~52	Average daily dose Proportion of patients who were able to reduce their average daily steroid dose by $\geq 25\%$ and ≤ 7.5 mg/day from baseline at Week 40~52 (in patients with baseline average daily steroid dose > 7.5 mg/day). Subjects who discontinued or completed administration of this drug before Week 52 will be classified as non-responders.

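### Read literally, the proteinuria item can fall from 4 to 0 with proteinuria unchanged, which alone meets the SELENA SLEDAI response cut-off and clears that item from the LLDAS renal clause

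*SAP*

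**What the plan says.** Protocol Appendix 1 reproduces the SELENA SLEDAI instrument. Its proteinuria item, weight 4, is defined as "New onset or recent increase of more than 0.5 gm/24 hours". Other items are worded differently: rash, for example, is "Ongoing inflammatory lupus rash", and the other three renal items (casts, haematuria, pyuria) score on presence. No section in view says how proteinuria that persists unchanged is to be scored later, and no period is attached to *recent* for this item.

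SAP 4.10 defines a SELENA SLEDAI responder by a "≥ 4 decrease in score from baseline". SAP 6.4.1 bases the response rate on this definition. LLDAS item 1 requires a total of 4 or less and "no major active organ involvement (renal, central nervous system, cardiopulmonary, vasculitis, pyrexia) on SELENA-SLEDAI". Item 2 looks only for new signs. Items 3 to 5 concern the physician's global assessment (PGA), the corticosteroid dose, and immunosuppressant and other drug use. SAP 6.4.4 reports the share of patients with a fall in each organ domain, and SAP 4.11 places proteinuria in the renal domain.

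Protocol section 8, item 12, collects the "Protein/creatinine ratio" at the start of administration and at Weeks 24 and 52, or at withdrawal. The SAP summarises and plots it as a laboratory value (6.4.7, 6.4.15). It does not enter the response or LLDAS definitions.

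**The concern.** An item that scores only onset or increase can return to zero because time has passed, with no change in the underlying finding. Proteinuria is the clear case, because its weight equals the response cut-off. One lapsed item can therefore make a responder of a patient whose urine protein is the same as at baseline.

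Three outputs are exposed: the response rate, the renal-domain decrease and, in part, LLDAS. The plan describes no control group in which the effect could cancel. The one measurement that could reveal it, the protein/creatinine ratio, is tabulated separately and never cross-classified with response.

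**Working it through.** **Inputs.** Item weights from Protocol Appendix 1 (24 items, 105 points in total); response and LLDAS item 1 rules from SAP 4.10; organ domains from SAP 4.11. The plan states no figure on this point to reproduce.

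**Rule applied.** Fall = baseline total − later total. Responder if the fall is at least 4. LLDAS item 1 is met if the later total is 4 or less and no listed major-organ item is scored. In every row below, proteinuria itself is unchanged between visits.

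| Example patient | Baseline | Later | Fall | Responder | LLDAS item 1 |
|---|---|---|---|---|---|
| A. Proteinuria scored at baseline; low complement and anti-dsDNA persist | 4+2+2 = 8 | 2+2 = 4 | 4 | yes | met |
| B. Long-standing proteinuria, already 0 at baseline; same serology | 2+2 = 4 | 2+2 = 4 | 0 | no | met |
| C. As A, with haematuria persisting | 4+4+2+2 = 12 | 4+2+2 = 8 | 4 | yes | not met |
| D. As A, with new rash and mucosal ulcers | 4+2+2 = 8 | 2+2+2+2 = 8 | 0 | no | not met |
| E. Proteinuria scored at baseline; arthritis, rash and low complement persist | 4+4+2+2 = 12 | 4+2+2 = 8 | 4 | yes | not met |

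If unchanged proteinuria kept its 4 points, patient A would go from 8 to 8: fall 0, non-responder, LLDAS item 1 not met.

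**What the rows show.**
- Response on this item alone needs the item scored at baseline and no offsetting new points (A, C and E against D).
- Proteinuria at 0 on both occasions creates no false response but still passes the LLDAS renal clause (B).
- A persisting cast, haematuria or pyuria item blocks LLDAS item 1 (C).
- A remaining total above 4 also blocks it (E).
- In A, C and E the renal domain falls by 4, so each counts as a decrease in SAP 6.4.4.

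**Size, as an illustration only.** The documents give no item frequencies. Let p be the share scored for proteinuria at baseline, u the share of those who are unchanged with no offsetting items, and r the share of these who would respond through other items anyway. The gain in the response rate is p × u × (1 − r). The assumed ranges are p 10% to 40%, u 25% to 50% and r 30% to 50%.
- Lowest: 0.10 × 0.25 × (1 − 0.50) = 0.0125, about 1 percentage point.
- Highest: 0.40 × 0.50 × (1 − 0.30) = 0.14, or 14 percentage points.

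**The case against.** The instrument is a published one, and the SAP applies it as written. The scores come from investigators. The implementation guidance and CRFs 1 and 2, listed in Protocol section 16, are not in the reviewed text and may tell investigators how to score persistent proteinuria. This stands: the documents show that the fall can occur, not that it did. It is also why the standard score should stay first.

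The ratio is already summarised at the same time points, and PGA response is reported alongside. That gives some visibility, but group means cannot show which responders had an unchanged ratio.

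Several stronger readings are tempting and are not supported:
- **That other onset-type items share the problem.** Seizure, cranial nerve disorder ("New onset of sensory or motor neuropathy involving cranial nerves") and cerebrovascular accident also carry recent- or new-onset wording. But absence of a further seizure or stroke at Week 52 may be genuine absence of activity. Nothing shows an artefact comparable to a measured, unchanged protein level.
- **That patients are wrongly declared in LLDAS.** Passing the renal clause is not LLDAS; items 2 to 5 must also be met, including a PGA that does not depend on onset wording.
- **That the severe lupus nephritis subgroup is worst affected.** Protocol section 8, item 2, defines severity by level (proteinuria above 6 g/24 h or creatinine above 2.5 mg/dl), not by onset. Long-standing proteinuria would score 0 at baseline and give no false response.
- **That a ratio of 0.5 g/g is the instrument's own criterion.** Appendix 1 speaks of onset or an increase in g/24 h, not of a standing spot-ratio level.

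**Conclusion.** The point holds for the proteinuria item alone and on a literal reading of Appendix 1. An unchanged finding can move from 4 to 0, meet the response cut-off by itself and count as a renal-domain improvement. If no other renal item is scored, it also satisfies the renal part of LLDAS item 1. Neither document, as seen here, guards against this.

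The size cannot be determined from the documents. The range of about 1 to 14 points rests entirely on assumed inputs and should not be quoted as an estimate of bias. This is a case for inexpensive supplementary analyses, not for replacing the standard definitions.

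**What to change.** Keep the standard SELENA SLEDAI and LLDAS definitions as the first row. Add to SAP 6.4.2 and 6.4.4, from data already collected:

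1. The number of responders who reach the 4-point fall only because the proteinuria item went from 4 to 0, split by change in protein/creatinine ratio. If investigators did keep scoring persistent proteinuria, few of these responders should have an unchanged ratio, and that settles the matter.
2. A sensitivity response rate that keeps the 4 points unless the ratio has fallen by more than a margin fixed before analysis, shown over a small range of margins. The margin is needed because, with true proteinuria unchanged, a repeat reading is about as likely to be lower as higher. A rule that removed the points on any fall would do so for roughly half of the patients it is meant to catch.
3. The number of LLDAS achievers whose ratio at that visit is above 0.5 g/g, labelled as a sensitivity cut-off and not as Appendix 1's criterion.

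Where the ratio is missing, keep the recorded score and report how many patients this affects.

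Cost: SAP wording, some programming and a few more tables, with no new data. The drawbacks are missing ratios and sensitivity rates that may be slightly less favourable than the standard ones.

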4.11. SELENA SLEDAI Organ System Domain

Organ System ¹	Item	Score
Central Nervous System 1	Convulsion	8
	Psychosis	8
	Organic brain disorder	8
	Visual impairment	8
	Cranial nerve disorder	8
	Lupus headache	8
	Cerebrovascular disorder 1	8
Vascular 1	Vasculitis	8
Musculoskeletal	Arthritis	4
	Myositis	4
Renal System	Cylindruria	4
	Haematuria	4
	Proteinuria	4
	Pyuria	4
Mucocutaneous	Rash	2
	Hair loss	2
	Mucosal ulcer	2
Cardiovascular and Respiratory	Pleurisy	2
	Pericarditis	2

Organ System ¹	Item	Score
Immune system	Low complement	2
	Anti-dsDNA	2
General disorders 1	Pyrexia 1	1
Hematology 1	Platelets decreased	1
	White blood cell decreased	1

¹: Cerebrovascular disorder is included from the central nervous system to the vascular system. Delete general disorders and include pyrexia in the vascular system.

4.12. Average daily steroid dose

The average daily steroid dose will be prednisolone-equivalent (prednisolone conversion table: to be defined in a separate document) and the average daily steroid dose during the 7 days prior to and including the day of evaluation will be used. The mean value during the 7 days before treatment including the dose on the first day of treatment will be used as the baseline. If there is no information on steroid administration during the observation period, it will be handled as "0 mg." Data obtained after the end date of administration of this drug will not be used for tabulation.

The prednisolone conversion table will be updated when new drugs are added and fixed with the data at the time of DBF.

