*: Described in “2. IMPORTANT PRECAUTIONS (7)” in the Package Insert for subcutaneous use.

5. Pre-treatment drugs intended for SLE
Presence or absence of drugs intended for SLE and name of drugs, from 4 weeks before the start of administration to the day before the start
Biological preparations and cyclophosphamide (intravenous injection) except Benlysta will be monitored from 24 weeks before the start of administration to the day before the start.
6. Administration status of Benlysta
Administration route of Benlysta during the observation period (Regarding subcutaneous injection, record any of the autoinjector or syringe.), single dose, duration of administration, administration interval during each period, dosing frequency during each period, reason for revision of the Dosage and Administration and drug withdrawal
7. Concomitant drugs (SLE drugs)
Presence or absence of concomitant drugs (SLE drugs), name of drugs, during the observation period
For systemic steroids, the information about the presence or absence of concomitant use, name of drugs, administration route, daily dose (dose, unit), duration of administration, reason for revision of the Dosage and Administration will be collected. For cyclophosphamide, the information about the presence or absence of concomitant use and administration route will be collected.
8. Concomitant drugs (except SLE drugs)
Presence or absence of concomitant drugs intended for SLE (except SLE drugs), name of drugs, reason for administration, during the observation period
9. Concomitant therapies intended for SLE (except drugs)
Presence or absence of concomitant therapies intended for SLE (except drugs), name of therapies, during the observation period
10. Vaccination
Presence or absence of vaccination, type of vaccine, date of vaccination, during the observation period
11. Course of clinical symptoms
The information about the following items will be collected.

1) Safety of Estrogens in Lupus Erythematosus National Assessment SLE Disease Activity Index (SELENA SLEDAI)

Record the presence or absence of assessment, assessment date, results of assessment at the start date of administration*, Week 24 and 52 after the start of administration, or withdrawal/termination (See Appendix 1).

* : If no information is available about the results of assessment at the start date of administration, record the information closest to the start date in the results of SLE diagnosis to the start date.

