6.4.2. Changes in responder rates (LOCF) (Tables 3.021, 3.0211, 3.0212, 3.022, 10.2)

Analyzed:	Efficacy analysis population
Analysis details:	
The number of responders/non-responders and the responder rate will be calculated in chronological order for each efficacy endpoint (SELENA SLEDAI score, PGA score, LLDAS, reduction of steroid dose at Week 40~52). 95% confidence intervals will be calculated for assessment at discontinuation/completion (LOCF).
 
Data will also be summarized by the presence or absence of severe lupus nephritis, presence or absence of severe central nervous system lupus, and route of administration as reasons for this drug use.
 
For data at discontinuation/completion (LOCF), the same analysis will be performed by patient characteristic.
 
For steroid dose reduction at Week 40~52, subjects whose baseline average daily steroid dose is > 7.5 mg/day will be included.

Chronological order:	Week 24, Week 52, at discontinuation/completion (LOCF), and Week 40~52 (steroid dose reduction at Week

40~52)

Patient characteristics:	
• SELENA SLEDAI (baseline): $\leq 9, \leq 10$• Anti-dsDNA antibody (baseline) [IU/mL]: $<30, 30 \leq$• Complement Levels:
Low C3 and/or Low C4Other than the above• C3 (baseline) [mg/dL] ($<90, 90 \leq$)• C4 (baseline) [mg/dL] ($<10, 10 \leq$)• Use of steroids at the start of treatment: No, Yes• Baseline steroid [mg/day]: $\leq 7.5, 7.5 <$• Immunosuppressant use: No, Yes
--------------------------	--

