6.4.14. Time course of percent improvement in steroid group (Figure 3.05)

Analyzed:	Efficacy analysis population
Analysis details:	For the improvement rate of steroid treatment, Kaplan-Meier plots will be calculated with the time point when the dose of steroid becomes 7.5 mg/day or less or the dose of steroid from baseline becomes 50% or less as an event.
CONDITION:	Patients with baseline average daily steroid dose >7.5 mg/day will be included.

6.4.15. Changes in laboratory values (Anti-dsDNA, C3, C4, CH50, protein/creatinine ratio) (mean + SD) (Figure 3.06x)

Analyzed:	Efficacy analysis population
Analysis details:	For anti-dsDNA antibody, C3, C4, CH50, and protein/creatinine ratio, time-course plots of mean + standard deviation will be prepared for each item.
Chronological order:	Baseline, Week 24, and Week 52, and at discontinuation/completion (LOCF)

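### A short high-dose steroid course in the 7-day baseline window puts a low-dose patient in the above-7.5 mg/day group and makes a return to the unchanged dose look like a reduction

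*SAP*

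**What the plan says.** **Baseline and dose scale (SAP 4.12).** "The average daily steroid dose will be prednisolone-equivalent (prednisolone conversion table: to be defined in a separate document" (the table itself is not in the readable text). The baseline rule is: "The mean value during the 7 days before treatment including the dose on the first day of treatment will be used as the baseline". Later assessments also use a 7-day average, ending on the day of evaluation. The section sets no limit by route, dose or length of course. Upkeep of the table is described by drug only: "The prednisolone conversion table will be updated when new drugs are added and fixed with the data at the time of DBF".

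**Who enters.** SAP 6.4.2 restricts the Week 40-52 reduction analysis to "subjects whose baseline average daily steroid dose is" above 7.5 mg/day. SAP 6.4.8 (Table 3.11) and 6.4.14 (Figure 3.05) use the same condition, and it is the starting state for item 3 of Table 3.13 (6.4.10). SAP 6.7 repeats several tables, including Table 5.05, by class of starting dose, with a top class above 10 mg/day.

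**What counts as success.** In SAP 4.10 it is a fall of at least 25% from baseline to 7.5 mg/day or less at Week 40-52; anyone who stops Benlysta before Week 52 is a non-responder. In 6.4.14, "For the improvement rate of steroid treatment, Kaplan-Meier plots will be calculated", and the event is a dose of 7.5 mg/day or less, or at most half of baseline. That event carries no Week 52 condition.

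**What is recorded.** Protocol section 8, item 7, covers the observation period and lists for systemic steroids "name of drugs, administration route, daily dose (dose, unit), duration of administration". Item 5, for the time before the start, lists only "Presence or absence of drugs intended for SLE and name of drugs, from 4 weeks before the start of administration to the day before the" first dose. SAP 4.4.5, under prior and concomitant drugs, treats systemic steroids for SLE as dated records.

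**The concern.** The baseline is meant to show what the patient was taking before Benlysta could act. If Benlysta starts within a week of a short high-dose course, the 7-day mean reflects the course instead. Entry to the above-7.5 group depends on the baseline alone, so such a course can only admit patients who are already at target; it cannot remove any. The study has no comparator in which the same artefact would appear and cancel. The end of a course would then be tabulated as a steroid reduction on Benlysta, and the mean dose change would be pulled by a few very large baselines.

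**Working it through.** **Plan figure.** The documents give no rate, power or sample size for the steroid endpoints, so there is nothing to reproduce. I applied the SAP rules to assumed courses. I read the window as the seven days ending on Day 1.

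**Inputs from the documents:** the 7-day mean (SAP 4.12); entry above 7.5 mg/day (4.10, 6.4.2, 6.4.8, 6.4.14); success rule (4.10); percent change as change divided by baseline (5.2); target of 600 patients (Protocol section 4).

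**Assumed inputs:** maintenance dose *m*; extra prednisolone-equivalent *X* in the window; conversion factor 1.0 to 1.25; share *q* of patients affected.

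**1. Baseline.** B = (7m + X)/7. For m = 5 mg/day and 500 mg on three days, B = (35 + 1500)/7 = 219.3 mg/day. At an unchanged 5 mg/day the apparent fall is 1 − 5/219.3 = 97.7%.

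| Assumed course, m = 5 | Baseline, mg/day (factor 1.0 to 1.25) | Apparent fall at unchanged 5 mg/day |
|---|---|---|
| 100 mg, one day | 19.3 to 22.9 | 74% to 78% |
| 250 mg, three days | 112 to 139 | about 96% |
| 500 mg, three days | 219 to 273 | 97.7% to 98.2% |
| 1000 mg, three days | 434 to 541 | about 99% |

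**2. Smallest course that suffices.** Entry needs X > 7(7.5 − m); the 25% rule needs X ≥ 7(m/0.75 − m). The larger of the two is: above 52.5 mg for m = 0, above 35 mg for m = 2.5, above 17.5 mg for m = 5, and at least 16.3 mg for m = 7.

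**3. When it counts.** In Figure 3.05 and Tables 3.11 and 3.13, as soon as the dose is back at maintenance. In the Week 40-52 responder rate, only if the dose is also at 7.5 mg/day or less then and Benlysta continues to Week 52.

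**4. Absolute mean change (Table 3.12x).** Each affected patient adds −X/7. With X = 1500 the shift is −q × 214.3: −2.1 mg/day at q = 1%, −4.3 at 2%, −10.7 at 5%. In the top class of Table 5.05 the same patients are a larger share, so the distortion is more concentrated.

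**5. Mean percent change.** A fall cannot exceed 100%. The shift is about q × 97.7: 1.0 point at q = 1% and 4.9 points at 5%.

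**6. Week 40-52 responder rate.** Assume that 45% of 600 are truly above 7.5 mg/day (270), that 40% of them succeed (108), and that 90% of wrongly admitted patients succeed. Wrongly admitted = 600 × q × 0.55.

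| q | Wrongly admitted | Rate |
|---|---|---|
| 1% | 3.3 | (108 + 2.97)/273.3 = 40.6% |
| 2% | 6.6 | (108 + 5.94)/276.6 = 41.2% |
| 5% | 16.5 | (108 + 14.85)/286.5 = 42.9% |

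In general the rate is (1 − f)p + f·r, where f is the wrongly admitted share of the group, p the rate in the rest and r the success share of those admitted. With f = 5%, p = 40% gives 41.5% (r = 0.7) or 42.5% (r = 0.9); p = 20% gives 22.5% or 23.5%.

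**The case against.** The strongest reply is that the documents never mention pulse courses, so the frequency and every size above rest on assumption. The responder shift is also small: with 270 patients and a rate of 40%, the 95% half-width is 1.96 × √(0.4 × 0.6/270) = 5.8 points, more than the 2.9 points at q = 5%. No readable success criterion depends on this endpoint. Medians and quartiles are already planned (SAP 5.1), as is cumulative dose (6.4.11). All of this stands. It limits the size of the problem but does not remove the one-directional selection or protect the mean change.

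A second reply concerns data and unseen documents. Protocol section 8 lists route and dose for the observation period only. If pre-start doses are not collected, only a course reaching Day 1 could enter the baseline. The conversion table and the definition of the steroid class (SAP 4.8, 4.12) are in separate documents, and a route rule there would settle the matter. This also stands, although a 7-day pre-treatment mean cannot be computed without pre-start doses.

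Three stronger readings are tempting and are not supported:

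- That the end of a course is enough for a Week 40-52 responder. SAP 4.10 also requires the dose at Week 40-52 and treatment to Week 52.
- That a few patients could dominate the mean percent change. The definition in SAP 5.2 bounds each fall at 100%.
- That intravenous steroid should be taken out of all averages. That would hide a course given at Week 40-52, which the present rule counts against success, and it would still miss short oral courses.

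**Conclusion.** The point holds. As written, SAP 4.12 lets a short course define the baseline, so a patient whose maintenance dose never changed can count as reduced. The absolute mean change is the output most exposed: about −2.1 mg/day for each 1% of patients with an assumed 500 mg on three days, scaling with the dose and share assumed. The mean percent change moves by about 1 point per 1%. The responder rate rises by about 0.6 to 2.9 points for 1% to 5% affected, given the assumed 45%, 40% and 90%; a lower underlying rate makes the rise larger.

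A reader might infer that the steroid results are largely an artefact. The documents do not support that: they do not show that any such course occurred in the baseline window. The conclusion also assumes that pre-start doses are held, or that a course reaches Day 1, and that no route rule sits in the separate documents. A course in a later window works the other way, towards apparent failure.

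**What to change.** Keep the all-route average as the main analysis, in the baseline and in the follow-up windows, so that later courses still count against success. Add to SAP 4.12:

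- a count of patients with intravenous steroid in the baseline window;
- a sensitivity analysis of the Week 40-52 responder rate, Figure 3.05 and Tables 3.11 to 3.13 and 5.05 that omits those patients, or that takes only their baseline from non-intravenous steroid.

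Reconcile Protocol section 8, item 5 (names of pre-start drugs only) with SAP 4.12 and 4.4.5 (which imply dated pre-start steroid doses). Confirm that the conversion table and the steroid class definition hold no route rule, or state the rule in 4.12 if they do.

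The cost is SAP wording, a route flag and one extra steroid summary. It depends on route being recorded for the pre-start days, and a route flag will not find short oral courses. If the count is zero, one sentence in the report closes the question for intravenous courses.
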